4. OBJECTIVES AND ENDPOINTS

OBJECTIVES	ENDPOINTS
PRIMARY	
The primary objective of the study is to assess the safety and tolerability of Siponimod in mild AD dementia subjects.	Safety will be assessed at each study visit through completion of comprehensive tests and procedures aimed at monitoring for potential adverse events (AEs). Study staff will also gather direct reports from subjects regarding any adverse events.
SECONDARY	
The secondary objective of the study is to assess the effects of Siponimod on AD-associated neurodegeneration by deriving annual brain atrophy rates from volumetric MRI (vMRI).	Siponimod was observed to slow rates of brain atrophy in both RRMS and SPMS patients. Thus, the aim is to assess the medical benefits of the drug in mild AD dementia subjects by assessing whether brain atrophy slows with Siponimod treatment. Subjects will undergo volumetric MRI (vMRI) measurements of the hippocampus, cortical thickness, and global thickness as indicators of neurodegeneration.
TERTIARY	
The tertiary objective of study is to assess the effects of Siponimod on cognition following administration of study drug vs. placebo.	Cognition will be assessed by comparing the changes in two assessments: ADCS-ADL and ADCOMS from baseline to various visit timepoints, including Week 78 (End of Study).
EXPLORATORY	
Exploratory objectives will include:	
i) measurements of markers found in the CSF fluid that are known to be associated with mild AD dementia and inflammation before and after treatment	i) CSF biomarkers that will be assessed include amyloid beta 40 & 42, Tau, and Phospho-Tau.
ii) assessment of blood inflammatory markers before and after treatment	ii) Blood inflammatory markers include CRP, TNF- α , IL-1 β , IL-6, IL-8, and IL-10 (54-plex measured on the Meso Scale Discovery [MSD] ELISA platform). Plus, we will count the number of white blood cells (B and T lymphocytes, macrophages, etc) in the blood to estimate the impact of Siponimod on peripheral markers of the immune system.
iii) to assess levels of A β found in saliva samples collected before and after treatment with Siponimod vs. placebo	iii) Saliva markers that will be assessed are A β 40 and A β 2. Saliva A β levels is a recent biomarker that has been identified to study AD. Thus, we propose to explore the effects of Siponimod on A β 40 and A β 2 throughout the course of the study.

5. STUDY DESIGN

OVERALL DESIGN

In the current project we aim to test the **central hypothesis that Siponimod could lower the rate of neurodegeneration as measured by brain atrophy in mild AD dementia subjects**. To test our central hypothesis, we will carry out an 18-month Phase II, double-blind, randomized, two-armed, placebo controlled, proof-of-concept clinical study in 105 mild AD dementia subjects who will receive an escalating dose of Siponimod (0.25-1 mg/day) or placebo at a randomization ratio of 2:1 for 12 months, followed by a 6-month washout period. For patients who meet inclusion/exclusion criteria, 35 will be randomly assigned to the placebo group, and 70 will be randomly assigned to the drug arm. A single site will manage the entire study, i.e. the Barrow Neurological Institute (BNI) in Phoenix, AZ. No patient stratification and no interim analysis are planned. The decision to pursue dosing will depend on safety data which is included in the inclusion/exclusion criteria.

6. SCIENTIFIC RATIONALE FOR STUDY DESIGN

This is a randomized, double-blind, placebo-controlled, parallel group study. The use of placebo is appropriate to minimize bias related to treatment expectations of the subject, study partner, and site investigator, as well as bias related to changes in the relationship between the subject and study partner that might occur with the initiation of treatment and expectation of improvement in motor symptoms or cognition. Changes in subject /study partner interactions can impact subject mood and might introduce biases that cannot be quantified. The double-blind use of placebo will also prevent bias in the clinical and scientific assessments.

Most monotherapy clinical trials with a focus on disease modification completed to date have failed to meet the clinical endpoint of significantly slowing cognitive decline in dementia due to Alzheimer's disease (AD), including BACE1 inhibitors⁴⁰, γ -secretase inhibitors and modulators¹⁸, and active and passive immunization against monomeric, oligomeric, and protofibril A β ²⁶. Recently the mABs, aducanumab and lecanemab, were approved on the biomarker endpoints of removing amyloid. This emphasizes the urgent need for novel therapeutic approaches able to reduce several AD neuropathologies simultaneously.

Inflammation is prominent in many neurological disorders, yet no clinical trial has demonstrated the efficacy of anti-inflammatory agents for AD. Interestingly, chronic peripheral low-grade inflammation is associated with aging and increases the risk for disease and mortality, including the development of AD²⁰. Accumulating evidence indicates that nuclear factor- κ B (NF- κ B), tumor necrosis factor alpha (TNF- α), interleukins (e.g. IL-1 β , IL-2, and IL-6), and chemokines (e.g. IL-8) were found elevated both in the blood and central nervous system (CNS) of AD patients²⁰. These data confirm that inflammation plays a critical role in the cause and effect of AD neuropathology⁴². Interestingly, Siponimod is capable of modulating inflammation by preventing egression of lymphocytes from lymphoid organs, and the modulation of cytokine expression, including in microglia⁵.

The use of the NIA-AA criteria³² is well-established and accepted for the diagnosis of mild AD. Nonetheless, we will use eventual updates released by the NIA for the diagnosis of AD throughout the duration of our clinical study.

Safety will be assessed by standard measures throughout the study.

The endpoints are appropriate measures of treatment effect in this study. Because no cognitive data has been reported in MS subjects, the main proxy for Siponimod efficacy is a slowing of neurodegeneration assessed by calculating annual brain atrophy rates. However, it is widely accepted in the neuroscience community that altering neurodegeneration will likely slow cognitive decline. To date, the main measure for an effective treatment of AD is cognitive performance. Indeed, while they may be useful to help with the diagnosis of AD, there is no biomarker that has demonstrated theragnostic value yet. Therefore, any inflexion of cognitive decline, as measured by the several tests we have selected, will be the only clinical validation of disease improvement. Thus, we have included the ADCOMS scale to assess cognition during our study.

Blood, saliva and CSF biomarkers were chosen for this study because they are expected to provide insights into inflammations status before, during and after dosing. As previously noted, the biomarkers being evaluated have been linked as being indicators for the progression of mild AD dementia.

JUSTIFICATION FOR DOSE

Dosing of Siponimod in AD is limited by two parameters. First, although no bradycardia was observed in a chronic high dose regimen in healthy subjects³⁸ and at therapeutic doses in MS patients undergoing a daily dose-titration regimen²⁷, these data were collected on young to middle-aged adults (age range 18-60). However, there is no literature on the possible cardiac AEs induced by Siponimod in older adults (age >60), which favors using a low dose in such individuals. Second, the *CYP2C9*2* and *CYP2C9*3* alleles are known to metabolize Siponimod more slowly than the *CYP2C9*1* genotype (half-lives of ~51 [double] and 126 hours [quintuple], respectively). *CYP2C9*2* allele is observed in 4-18% of Caucasians and Hispanics, which constitute a large proportion of the AD patients seen at BNI, and *CYP2C9*3* allele has a frequency of 2-20% in the same ethnicities, while Asians, African decedents, and Native Americans have lower frequencies for both genotypes^{33,43}. These observations of moderate frequencies for *CYP2C9*2* and *CYP2C9*3* alleles, and the recommendations from the FDA-approved package insert encourage us to administer the suggested low dose of 1 mg/day in *CYP2C9*1/x* and *CYP2C9*2/x* subjects, and to exclude *CYP2C9*3/3* subjects (0.4-0.5% of the population) for the present study. Consequently, and after discussing these issues with our MS specialty colleagues, for safety reasons we have selected to administer a maximum dose of 1 mg/day to the mild AD subjects that we will enroll in this proof-of-concept study. Further, instead of the daily titration regimen recommended in MS, we will apply a biweekly dose increment of 0.25 mg/day over the course of 6 weeks, with the first dose given at each increased strength (dose increases by 0.25 mg at a time) taken during in-person visits at BNI to monitor for any eventual AEs that could emerge with dose increases.

END OF STUDY DEFINITION

A participant is considered to have completed the study if he or she has completed all phases of the study including the last visit or the last scheduled procedure shown in the Schedule of Events (SOE).

7. STUDY POPULATION

INCLUSION CRITERIA

See table on page 5 for *inclusion*/exclusion criteria.

EXCLUSION CRITERIA

See table on page 6 for inclusion/*exclusion* criteria.

LIFESTYLE CONSIDERATIONS

Because of its ability to inhibit CYP enzymes, study subjects will be recommended to not eat grapefruit or drink grapefruit juice.

SCREEN FAILURES

Screen failures are defined as participants who consent to participate in the clinical trial but are not subsequently randomly assigned to the study intervention or entered in the study. The collection of a minimal set of screen failure information is required to ensure transparent reporting of participants who are deemed as a screen failure, to meet the Consolidated Standards of Reporting Trials

(CONSORT) publishing requirements and to respond to queries from regulatory authorities. Minimal information includes demographics and eligibility criteria.

Because of inherent daily variations in cognitive performance observed in the clinic, if MMSE score is outside of the range 20-26 at the initial screening, the PI may request MMSE retesting after a two week period.

Patients who do not meet one or more of the entry criteria will not be randomized and will be considered screen failures. Screen failures may be re-screened once per PI discretion for eligibility.

STRATEGIES FOR RECRUITMENT AND RETENTION

The clinical trial aims to recruit a total of 105 subjects from the study site, Barrow Neurological Institute (BNI). Study goal is to achieve a balanced enrollment, targeting approximately 50% male and 50% female participants. These study subjects will be outpatients diagnosed with mild AD dementia at BNI.

In Arizona, there are an estimated 150,000 cases of AD¹. Annually, BNI sees approximately 2,000 patients with memory disorders. Most patients are Caucasians, but our clinics have representative samples of URGs including LatinX and African Americans, though we consistently work to reach other members of Underrepresented Groups as well. Recently, for the New IDEAS (Imaging Dementia-Evidence for Amyloid Scanning) study, we enrolled 27 participants, all of whom belong to URGs (underrepresented racial and ethnic groups). This patient population has eagerly engaged in clinical trials, and BNI has approximately 30 clinical trials on-going at any given time. The majority of the current clinical trial participants are referred by BNI physicians, with a small percentage referred by community physicians and agencies. The BNI research team has consistently met or exceeded their patient enrollment targets over the past ten years with over 600 clinical trial participants in the current database. Patients followed at BNI are continuously offered opportunities to be screened for clinical trials.

[figure not shown]
To maximize retention, we will use several methods to contact participants (phone, email, family contact) and give visit reminders. Our study design was also adapted to improve retention by offering flexibility for the scheduled in person visits (± 7 days), and by including longer in person visit intervals in the final 6 months of dosing. We have consulted MS specialists to identify the minimum dose possible to retain efficacy while minimizing adverse events, which we hope will prevent early withdrawals.

8. STUDY INTERVENTION

STUDY INTERVENTION(S) ADMINISTRATION

STUDY INTERVENTION DESCRIPTION

Siponimod is marketed by Novartis Pharmaceuticals Corporation under the name “Mayzent” registered under FDA IND #076122 (initially named “BAF-312”). The empirical formula is C₂₉H₃₅F₃N₂O₃, and the gram molecular weight is 516.6. Its chemical structure is shown below.

The formulation used in the present study will be provided by Novartis and is the same as indicated in IND #076122:

“Siponimod is provided as 0.25 mg film-coated tablets for oral use. Each film coated tablet contains 0.25 mg Siponimod, equivalent to 0.2 mg as Siponimod fumaric acid co-crystal. Siponimod film-coated tablets contain the following inactive ingredients: microcrystalline cellulose, crospovidone, glyceryl behenate, lactose monohydrate, colloidal silicon dioxide with a film coating containing lecithin (soy), iron oxides (red and black iron oxides for the 0.25mg), polyvinyl alcohol, talc, titanium dioxide, xanthan gum.”

Similarly, the placebo formulation will be provided by Novartis as explained in IND #076122: “The placebo tablets used in the studies described in this NDA have the same composition and configuration as the 0.25 mg drug products but do not contain Siponimod.”

DOSING AND ADMINISTRATION

The primary objectives of our project are the examination of drug safety and tolerability. This is an 18-month Phase II, double-blind, randomized, two-armed, placebo controlled, proof-of-concept clinical study. In total, we will enroll 105 early symptomatic AD subjects (i.e. mild AD) who will receive an escalating dose of Siponimod (0.25-1 mg/day) or placebo at a randomization ratio of 2:1 for 12 months (52 weeks), followed by a 6-month washout period (month 18). Study medications will be given orally, preferably in the morning. The patients and study staff will be blind to the randomization schema. For patients who meet all inclusion and exclusion criteria for enrollment, 35 will be randomly assigned to the placebo group, and 70 will be randomly assigned to the drug arm. There is no visual, taste, or smell difference between the placebo and Siponimod formulations. The randomization schedule will be developed by the study biostatistician.

For safety reasons, a gradual dose escalation regimen will be implemented for mild AD dementia subjects receiving Siponimod/Placebo. The medication will be administered in 0.25 mg increments biweekly reaching the maximum dose of 1 mg. As a precaution, the initial higher doses will be given in a clinical setting, with subjects observed for six hours by study staff who are blinded to the study drug. This allows for prompt intervention in case of any distress, such as issues with heart or blood pressure. During these in-person visits, blood samples will be collected to monitor for signs of toxicity changes. Tests will include a complete blood count with differential, comprehensive metabolic panels, and liver function.

All test results will be reviewed by the principal investigator (or sub-investigators) to determine whether toxicity is developing in study subjects. Moreover, we will carry out cognitive tests every 3 months and volumetric MRI every 6 months (Table 1) to detect eventual brain toxicities. Finally, in case of AEs outside of the clinic, Study subjects will be provided contact information for both clinic and study coordinator.

The investigator or his designee is responsible for explaining the correct use of the investigational agents to the patient/caregiver/study partner, verifying that instructions are followed properly per drug manufacturer. Study staff will maintain accurate records of investigational product dispensing and collection and returning all unused medication to the Study Site at each in-person visit. Patients will be instructed to contact the investigator or the study coordinator as soon as possible if he or she has a complaint or problem with the investigational product so that the situation can be assessed.

If toxicities are identified, we will apply a special toxicity protocol. Per clinical trials, hepatotoxicity was primarily noted in controlled trials of Siponimod in patients. Notably, AST and ALT values were elevated above 3 times the upper limit of normal. If hepatotoxicity is noted, the subject will be withdrawn from the study and not replaced if this occurs after Visit 7. Please refer to the section, Procedure Used in Case of Toxicity.

PREPARATION/HANDLING/STORAGE/ACCOUNTABILITY

ACQUISITION AND ACCOUNTABILITY

For this study, we will acquire a clinical trial form of 0.25 mg Siponimod from Novartis, the same formulation as used in clinical trials for multiple sclerosis (IND #076122). During the time between reception from the drug manufacturer to the delivery to study subjects, the study drug and placebo will be managed solely by licensed pharmacists from the investigator's institution (i.e., BNI). The shelf life of Siponimod being 18 months per manufacturer's recommendation, several batches of investigational products (Siponimod and matching placebo) are planned to cover the need of study drug for the entire duration of the study.

To maintain the blind of the blinded staff including the blinded monitor, there will be a separate unblinded pharmacy monitor to review the unblinded pharmacy records. [name], from the Barrow Neurological Institute will serve as the unblinded pharmacy monitor for this study.

The unblinded pharmacy monitor will have access to the unblinded pharmacy records and will perform accountability of the investigational products at each onsite monitoring session. Verification of the investigational products includes documenting any discrepancies between the total amounts of study drug shipped to the study site with the total amount of study drug dispensed to subjects along with unused study drug. The monitor will verify that correct study drug was administered by comparing study record against pharmacy documentation.

The unblinded pharmacy monitor will perform the following checks and verifications:

- Confirm study drug was administered only to qualified subjects who provided written Informed Consent.
- Confirm all study drug used for each subject and verify dispense dates.
- Check for site pharmacy personnel changes. If changes occur, ensure new personnel will have access to receive the study drug during the trial.
- Review temperature logs. Ensure the correct temperature is maintained.
- Ensure the receipt of drug shipments has been acknowledged by the Pharmacy on Record, and packing lists are filed.
- Verify that the investigational products are stored in a securely locked area.

At the end of the study, all unused study drugs will be reviewed by the unblinded pharmacy monitor and disposed of as directed by standard local procedures. A final drug inventory log will be retained at the study site.

FORMULATION, APPEARANCE, PACKAGING, AND LABELING

Formulation

Siponimod is an analogue of fingolimod. It is an immunomodulatory agent that binds with high affinity to the sphingosine-1-phosphate (S1P) receptors S1P1 and S1P5 subtypes of the five known S1P receptors. The chemical name is 1-[[4-[(E)-N-[[4-cyclohexyl-3-(trifluoromethyl)phenyl]methoxy]-C-methylcarbonimidoyl]-2-ethylphenyl]methyl]azetidine-3-carboxylic acid. The empirical formula for Siponimod is C₂₉H₃₅F₃N₂O₃, and the gram molecular weight is 516.6.

Active ingredient: Each 0.25 mg tablet contains 0.2 mg of Siponimod.

Excipients: The excipients are microcrystalline cellulose, crospovidone, glyceryl behenate, lactose monohydrate, colloidal silicon dioxide with a film coating containing lecithin (soy), iron

oxides (red and black iron oxides for the 0.25mg strength), polyvinyl alcohol, talc, titanium dioxide, xanthan gum.

Appearance

Siponimod is white to almost white powder. It is soluble in warm water up to 100 mg/mL.

Packaging

Siponimod and matching placebo tablets will be manufactured and packaged in USP compliant child-resistant bottles by Novartis with 14 tablets per bottle. Bottles will be directly shipped by Novartis to the BNI pharmacy at regular intervals.

Placebo

Matching placebo tablets used in this study will have the same composition as the 0.25 mg drug products but do not contain Siponimod. The matching placebo will be of identical appearance to the study medication to maintain the double-blind design of the study.

Labeling

Study drug will be labeled in accordance with GCP and local regulations. Each bottle containing study drug or placebo will be labeled with the following information:

- Protocol number
- [Subject name], [Subject number], [DOB]
- [Date of dispensation]
- Siponimod 0.25 mg or Placebo Tablets
- Instructions on taking medications as directed by physician
- Lot number/kit number
- Expiration date
- Store at refrigerated at 4°C (with excursions permitted to 2-10°C)
- Name, address, and phone number of the principal-investigator
- "Investigational Drug Use Only"

PRODUCT STORAGE AND STABILITY

Manufacturer shelf-life is 18 months. We will be acquiring the study drug from Novartis in small batches over a period of 5 years. Study drug will be stored in a refrigerator (4°C) with excursions permitted to 2-10°C. The tablets should not be exposed to high temperature and humidity. Tablets should be protected from light. Temperature will be monitored and recorded to ensure the stability of study drug. Expiry dates will be monitored, and any expired products will be pulled from the active stock.

PREPARATION

Siponimod and matching placebo tablets of the same size and color to the active drug will be compounded by Novartis in accordance with GCP (IND #076122). The matching placebo will be of identical appearance to the study medication to maintain the double-blind design of the study.

MEASURES TO MINIMIZE BIAS: RANDOMIZATION AND BLINDING

This is a randomized, double-blind, placebo-controlled, parallel group study. The use of placebo is appropriate to minimize bias related to treatment expectations of the subject, study partner, and site investigator, as well as to changes in the relationship between the subject and study partners that might occur with the initiation of treatment and expectation of improvement in motoric symptoms or cognition. Changes in subject/study partner interactions can impact subject mood and might introduce biases that

cannot be quantified. The double-blind use of placebo will also prevent bias in the clinical and scientific assessments.

Randomization will be carried out by our study biostatistician and the medication or placebo prepared accordingly by our clinical pharmacist. This procedure was developed to ensure double blinding, i.e. neither the investigators, nor the study subjects will know the medication taken by study subjects until the completion of the study and the acquisition of all data.

Emergency unblinding for AEs will be performed by the unblinded pharmacy team if the subject's well-being requires knowledge of the subject's treatment assignment. The subject's treatment status will remain blinded to other study personnel and Principal Investigator.

The investigator should make every effort to contact the medical monitor prior to unblinding a subject's treatment assignment. If a subject's treatment assignment is unblinded, the medical monitor and DSMB must be notified immediately. All unblinding events will be recorded in the CRF.

At the baseline visit (Visit 2), subjects who have met all the eligibility criteria for enrollment will be randomly assigned to one of two treatment groups:

1. Placebo (n=35) or
2. Siponimod 1 mg/day (n=70)

Randomization will be 2:1 and designed by our biostatistician. Randomization will take place during the Baseline visit.

In case of toxicity finding, the blinding will remain in effect as neither the Investigator, nor site staff will be informed whether the participants receive Siponimod or placebo. However, the study pharmacist will be informed in case there is need to adjust dosing if participants are treated with investigational product.

An independent statistician supporting the DSMB will be unblinded and may unblind the DSMB if required for proper study monitoring. All staff and research personnel involved in this study will remain blinded until all subjects have completed the trial and scientific data acquired.

STUDY INTERVENTION COMPLIANCE

Patient compliance with study medication will be assessed at each visit. Compliance will be assessed by direct questioning and counting returned tablets. Deviation(s) from the prescribed dosage regimen should be recorded in the CRF.

Patients who are significantly noncompliant will be instructed to discontinue medication from the study. A patient will be considered significantly noncompliant if he or she misses more than 21 consecutive days of study medication during the study without extenuating circumstance, for example: development of an SAE. Patients who stop dosing due to development of an SAE will have their case reviewed by investigator, site, medical monitor, DSMB, and Principal Investigator for prescribing appropriate actions. Similarly, a patient will be considered significantly noncompliant if he or she is judged by the investigator to have intentionally or repeatedly taken more than the prescribed amount of medication. Drug accountability will be emphasized at the start-up meeting, and drug accountability will be monitored throughout the study.

Temporary discontinuation of treatment with study drug due to ARIA-E should not be considered as non-compliance.

CONCOMITANT THERAPY

All concomitant medications taken during the study must be recorded on the concomitant medications case report form (CRF). Patients and their study partners/ caregivers will be instructed to consult the investigator or other appropriate study personnel at the site before initiation of any new medications or supplements and before changing dose of any current concomitant medications or supplements.

Medications that may affect cognitive function should be discussed with the medical monitor to determine if the patient should remain in the study.

- Allowed Concomitant Therapy

Patients on stable standard of care (SoC) AD treatment will be allowed in the study. The patient can be on stable doses of a cholinesterase inhibitor and/or memantine if it is stable for at least 90 days prior to the screening visit and is expected to remain on a stable dose for the remainder of the study period; or have demonstrated intolerance to or lack of efficacy from these medications.

- Prohibited Concomitant Therapy

Any therapy that does not fit with the SoC will be prohibited, including, but not limited to, cancer chemotherapy, narcotics, antimanic, and any anticonvulsants/antiseizures taken specifically for seizure disorders or epilepsy, and drugs listed in the exclusion criteria.

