Statistical analysis of the biomarkers and clinical assessments will be carried out by our biostatistician. Comparisons will assess the change from baseline for the following markers assessed at the frequency indicated in the schedule of visits Table 1):

- vMRI, which is used to estimate the annual rate of brain atrophy.

ANALYSIS OF THE SECONDARY ENDPOINT(S)

Statistical analysis of the biomarkers and clinical assessments will be carried out by our biostatistician. Comparisons will assess the change from baseline for the following markers assessed at the frequency indicated in the schedule of visits Table 1):

- Alzheimer's Disease Assessment Scale - Cognitive (ADAS-Cog13);
- Clinical Dementia Rating-Sum of Boxes (CDR-SOB);
- Mini Mental State Examination (MMSE);
- ADCOMS, which is calculated using components of the three cognitive tests indicated above.

SAFETY ANALYSES

- Concomitant Medications

Concomitant medications will be coded by the World Health Organization (WHO) Drug Dictionary and tabulated by the treatment group.

- Adverse Events

The incidence of all treatment-emergent AEs (TEAEs) and treatment-related AEs will be tabulated by treatment received. These AEs will be classified by system organ class and preferred term using the Medical Dictionary for Regulatory Activities (MedDRA). For incidence reporting, if a subject reported more than one AE that was coded to the same system organ class or preferred term, the subject will be counted only once for that specific system organ class or preferred term. A TEAE is defined as an event that first occurs or worsens in intensity after the administration of study drug. Events recorded between the time the informed consent is signed and the first study drug administration will be listed.

An overview of AEs, which includes subject incidence of TEAEs, treatment-related AEs, SAEs, deaths, and AEs leading to discontinuation, will be presented. For AEs presented by severity, the worst severity during the study will be presented for each subject.

The subject incidence of TEAEs and treatment-related AEs will be summarized by system organ class and preferred term.

- Serious Adverse Events

All SAEs will be listed and summarized in a similar manner to AEs.

- Clinical Laboratory Results

Clinical laboratory values will be measured by a central laboratory.

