All research activities will be conducted in as private a setting as possible.

The study monitor, other authorized representatives of the sponsor, representatives of the Institutional Review Board (IRB), regulatory agencies or pharmaceutical company supplying study product may inspect all documents and records required to be maintained by the investigator, including but not limited to, medical records (office, clinic, or hospital) and pharmacy records for the participants in this study. The clinical study site will permit access to such records.

The study participant's contact information will be securely stored at the clinical site for internal use during the study. At the end of the study, all records will continue to be kept in a secure location for as long a period as dictated by the reviewing IRB, Institutional policies, or sponsor requirements.

Study participant research data, which is for purposes of statistical analysis and scientific reporting, will be transmitted to and stored at the study biostatistician. This will not include the participant's contact or identifying information. Rather, individual participants and their research data will be identified by a unique study identification number. The study data entry and study management systems used by clinical sites and by research staff will be secured and password protected. At the end of the study, all study databases will be de-identified and archived at BNI/Dignity Health, Phoenix, AZ.

FUTURE USE OF STORED SPECIMENS AND DATA

Data collected for this study will be analyzed and stored at BNI, Phoenix, AZ. After the study is completed, the de-identified, archived data will be transmitted to and stored at BNI, Phoenix, AZ, for use by other researchers, including those outside of the study.

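### The study biostatistician runs the randomisation, stores the research data and analyses efficacy, so the stated blinding of all personnel does not hold for that role

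*Protocol*

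**What the plan says.** Four kinds of task go to one role, called the study biostatistician or our biostatistician.

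- **Making the schedule.** Section 8, Dosing and Administration: "The randomization schedule will be developed by the study biostatistician". Later in section 8: "Randomization will be 2:1 and designed by our biostatistician".
- **Running it.** Section 8, Measures to Minimize Bias: "Randomization will be carried out by our study biostatistician and the medication or placebo prepared accordingly by our clinical pharmacist".
- **Holding the data.** Section 13, Confidentiality and Privacy, says that participant research data "will be transmitted to and stored at the study biostatistician".
- **Analysing it.** Section 12, under both the primary and the secondary efficacy endpoints: "Statistical analysis of the biomarkers and clinical assessments will be carried out by our biostatistician". The exploratory CSF, blood and saliva analyses go to the same role.

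On blinding, section 8 makes two broad statements: "The patients and study staff will be blind to the randomization schema" and "All staff and research personnel involved in this study will remain blinded until all subjects have completed the trial and scientific data acquired". It names as unblinded the pharmacy team and the pharmacy monitor, has the study pharmacist informed in case of toxicity, and makes an independent statistician supporting the DSMB unblinded. The study biostatistician is not listed.

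**The concern.** A person who writes the allocation list and carries out each assignment cannot be blind to it. If the same role also receives the outcome data and does the efficacy analysis, allocations and outcomes sit together on the analysis side before database lock. Blinding the analyst until lock protects the choices that are not yet fixed at that stage. If those choices can be made with the arms visible, a reader of the results cannot rule out that they were shaped by the data, even when everyone acted properly. The protocol describes no masked codes, no separate randomisation statistician and no other barrier for this role.

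**Working it through.** No arithmetic on power or error rates applies. The check compares the statements about roles and then asks what is still open for an unblinded analyst to influence.

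1. **Can the blinding statement and the task list both hold?** There are two readings.
   - The biostatistician counts among the staff and research personnel. The section 8 blinding sentence then contradicts the section 8 sentences that give this role the schedule and its conduct.
   - The biostatistician does not count among them. The list of unblinded roles is then incomplete, and the efficacy analyst is unblinded with no restriction stated.

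   Under either reading section 8 needs amending.

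2. **Does the narrower definition of the double blind resolve it?** Section 8 explains the procedure as ensuring that "neither the investigators, nor the study subjects will know the medication taken by study subjects until the completion of the study". That covers investigators and subjects only. But the same section goes on to extend blinding to all research personnel, and Dosing and Administration extends it to study staff with respect to the schema itself. The narrower sentence does not cancel the broader ones.

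3. **Does the protocol separate these functions elsewhere?** It does. The pharmacy has a monitor distinct from the blinded monitor, and the DSMB has a statistician described as independent. Only the trial's own statistical role combines randomisation with analysis.

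4. **What is still open?**
   - *Efficacy set.* Section 12, Populations for Analyses, requires subjects to reach Visit 12 and labels that visit Week 8. In the Schedule of Events Visit 12 is Day 336, and 336 / 7 = Week 48. Week 8 is Day 56 (56 / 7 = 8), which is Visit 6. The two readings differ by 48 − 8 = 40 weeks. Replacement in section 9 turns on a third point, Visit 7, Day 70 (70 / 7 = Week 10). Someone has to settle which randomised subjects count.
   - *MRI measure.* Sections 4 and 10 name hippocampal, cortical and global measures without ranking them. The primary efficacy analysis in section 12 says only that volumetric MRI is used to estimate the annual rate of brain atrophy.

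5. **When does access arise?** Subjects are randomised one at a time at Baseline (Visit 2.5 for those having a lumbar puncture). Access therefore builds up subject by subject and reaches the planned 70 + 35 = 105 when enrolment ends.

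**The case against.** The best reply has four parts.

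- **The text names a role, not a person.** Section 12 sends outcome measures to a named recipient at a university. The name is removed, so that recipient cannot be matched to whoever runs the randomisation. Section 13 says a Manual of Operations will set out roles, and an SAP may do so too. This stands as a limit: that one individual knows every allocation is an inference. It does not remove the point, because the protocol gives all the tasks to the same role title and separates no one.
- **The phrase about all staff is loose drafting.** The pharmacy exceptions already show it is not literal. That is fair, but the missing exception is the one that affects the efficacy analysis.
- **The consequence is bounded.** The primary objective is safety and tolerability, no formal interim analysis is planned, and this arrangement does not unblind those who dose subjects, rate cognition or assess adverse events. All of this stands and limits the weight of the point.
- **Timing is not stated.** The protocol does not say when data reach the biostatistician. Access while data accrue is what the roles permit, not something the text schedules.

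A reader might also infer more than the document supports:

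- *That this person decides data queries, exclusions and late scans.* No section says so. Section 13 gives data checking to the investigators with data-management support, the study monitor and system checks. The scan windows are set in the schedule.
- *That a false-positive rate can be computed from picking the best of several image-analysis outputs.* The long list of outputs in section 10 stands under the screening-scan heading. Such a figure would measure the cost of multiple measures, which a blinded analyst could incur equally after lock, so it does not measure this defect.
- *That all 105 allocations are known throughout the 4–5 years of the trial.* They become known one by one.

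**Conclusion.** The point holds as a conflict over roles within the protocol. Followed as written, the plan gives the efficacy analyst access to each allocation from the moment of assignment, together with outcome data, while stating that all personnel are blinded. The conclusion rests on two assumptions: that the study biostatistician and our biostatistician are the same function, as the shared title indicates, and that no barrier in an unseen document separates the people who fill it. The size of any resulting bias cannot be quantified from the protocol. The risk lies in the definition of the efficacy set and the choice of MRI measure, both still open in the text. It is worth correcting because those choices bear directly on the main efficacy result and the correction is cheap.

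**What to change.** Amend section 8 (Dosing and Administration; Measures to Minimize Bias) as follows:

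- The independent statistician supporting the DSMB, or the unblinded pharmacy team, generates and holds the 2:1 schedule and releases assignments to the pharmacist.
- The biostatistician who analyses efficacy stays blinded and receives the codes only at database lock.
- The sentence on blinding of all personnel is limited to the roles that are in fact blinded, and the unblinded roles are listed.

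If enrolment has begun, transfer the list, record the date, and disclose the earlier access when results are reported. Simply declaring the biostatistician unblinded would make the text consistent but leave the access in place. If that route is preferred, a different, blinded statistician should do the efficacy analysis.

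The cost is a protocol amendment and a small amount of extra work for a role already in the plan. Sample size, visits and assessments are unaffected.
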